6. STUDY OPERATIONS

6.1 Protocol Deviations

Protocol deviations will be listed separately for randomized subjects with information such as type of deviation, severity of the deviation (major or non-major), date of occurrence, the reason for the deviation, steps taken to address the deviation, and whether or not the deviation was reportable to the regulatory authorities. The number of major protocol deviations, the number of each type of violation, the number of consented subjects with at least one deviation, the number of deviations leading to termination of a subject from study and the number resulting in an AE will be summarized in a tabular format.

6.2 Treatment Compliance

Treatment compliance will be summarized by treatment arm through the total duration of blinded study therapy (12 months). In each of the treatment arms compliance rate will be calculated as follows: first we calculated the amount of days the participant should have taken the tablet from the start of the IMP until the last day of the IMP taken before switching to the open-label follow up treatment with Grazax. Then we calculated how many days the participant took the tablet according to the returned tablets counted by Pharmacy. We calculated the resulting difference between the amount of tablets that the participant should have taken to the actual amount of tablets taken (e.g. if the participant should have taken 100 tablets and he took 80 tablets it will be calculated as follows: $100:100 \times 80 = 80$ (this would be a compliance of 80 %).

Treatment compliance will be presented across treatment groups.

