6.3.7 Premature discontinuation of study therapy

Study therapy is defined as initiation of any of the study medications described in Section 6.4 Study therapies will be discontinued for any of the following reasons:

- Two or more occurrences of grade 3 or above systemic allergic reactions after administration of study therapy. Grade 3, per World Allergy Organization (WAO) criteria, is defined as severe asthma symptoms (over 40% drop in PEF or FEV₁) *not* responding easily to an inhaled bronchodilator, and/or laryngeal oedema with stridor.³⁵
- Any adverse event (AE) and adverse reaction (AR) that, in the judgment of the principal investigator or the medical monitor, presents an unacceptable consequence or risk to the participant.
- An illness or infection that is not associated with the condition under study and that requires treatment not consistent with protocol requirements; or, if a participant develops an intercurrent illness that in the judgment of the PI in any way justifies discontinuation.
- An inability or unwillingness to comply with the study protocol, with protocol deviations sufficient to jeopardize the participant's well-being or the integrity of the study.
- Pregnancy occurring during study participation.

Participants who prematurely discontinue study treatment will be invited to complete the planned study assessments throughout the duration of the trial. However, if they decline they will undergo a follow-up visit 24 hours after discontinuation. One week after the follow-up visit, they will be contacted by telephone and discharged from the study.

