6.4.3 Administration

The first Grazax® or Grazax® placebo will be administered under the supervision of the trial physician and the participant observed for one hour thereafter before discharge from the clinic. This will take place on Visit 1, which will be conducted 1 day after the

second baseline visit (V0b). Thereafter, home sublingual administration of Grazax® or Grazax® placebo tablets will occur daily during the 12 months of the trial. In those participants who received active treatment a continuation of daily treatment will take place for another 12 months. Those participants who received placebo will be offered 24 months of active treatment after completion of the first 12 months and after unblinding. Tablets should be removed from the blister packs with dry fingers and should be taken immediately after opening the blister. Each tablet should be placed underneath the tongue until fully dissolved (1–2 minutes). Swallowing should be avoided for about 1 minute. Food and beverage should not be consumed for the following 5 minutes. For additional information on the preparation and administration of Grazax®, please refer to the following uniform resource locator (URL):

http://www.grazax.com/SiteCollectionDocuments/Grazax.com/About%20Grazax/Grazax_SmPC_MRP_VAR13_15OCT2010.pdf

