6.8.2 Analysis samples

- **Intent-to-treat (ITT) sample** will be defined as all randomized participants. ITT participants will be analysed with the group to which they were randomized, regardless of the medication actually received. If participants drop out post randomisation, they will be invited to complete study assessments throughout the duration of the trial.
- **Per-protocol (PP) sample** will be defined as ITT sample participants who remain in the study for 12 months and in whom the primary endpoints were assessed. Participants in the PP sample must be compliant with study medication, defined as taking 75% or more of their study medication for the duration of the study. Compliance with study medication will be as assessed by pill count for AIT/placebo. Participants in the PP sample will be analysed with the group to which they were randomized.
- **Safety sample (SS)** will be defined as all randomized participants who received at least one dose of study medication. Participants in the safety sample will be analysed with the group according to the medication they actually received, regardless of their randomized assignment.

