3. ANALYSIS SAMPLES

- **Intent-to-treat (ITT) sample** will be defined as all randomized participants. ITT participants will be analyzed with the group to which they were randomized, regardless of the medication actually received. If participants drop out post-randomization, they will be invited to complete study assessments throughout the duration of the trial.
- **Per-protocol (PP) sample** will be defined as ITT sample participants who remain in the study until the primary endpoint was assessed. Participants in the PP sample must be compliant with study medication, defined as taking 75% or more of their study medication for the duration of the study. Compliance with study medication will be assessed by pill count for SLIT and placebo. Participants in the PP sample will be analyzed with the group to which they were randomized.
- **Safety sample (SS)** will be defined as all enrolled participants. Participants in the safety sample will be analyzed in regards to adverse events.

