5. STUDY SUBJECTS

5.1 Demographic and Other Baseline Characteristics

Summary descriptive statistics for baseline and demographic characteristics will be reported for the randomized atopic and non- atopic sample.

Demographic data will include and data will be adjusted for age, gender, Skin Prick test (screening), specific IgE (screening) and compliance.

Furthermore the following characteristics will be used for descriptive statistics only: baseline visual analogue scale (How has your Hayfever been overall in the previous season? (Appendix 2 from Protocol), Polisensitisation (this will be defined as a positive skin prick test during screening apart from skin prick test to timothy grass and the positive control (Yes/No), seasonal asthma, this information will be taken from the medical and allergy history from the participant (Yes/No), total IgE, BMI, ethnicity.

These data will be presented in the following manner:

- Continuous data (e.g., age) will be summarized descriptively by mean, SD, median, min, and max.
- Categorical data (e.g., sex and ethnicity) will be presented as frequencies and percentages.

Demographic and baseline characteristic data will also be presented in data listings by study group (atopic (placebo and active group) and non-atopic).

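### SAP 6.2 ends the compliance denominator on the last day IMP was taken, so an early stopper is scored on pre-stop adherence alone or, on the other reading, has no formula

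*SAP*

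**What the plan says.** SAP 6.2 opens by fixing the period: "Treatment compliance will be summarized by treatment arm through the total duration of blinded study therapy (12 months"). It then defines the days due as running "from the start of the IMP until the last day of the IMP taken before switching to the open-label follow up treatment with Grazax". The days taken come from the pharmacy count of returned tablets, and the rate is taken over due. There is no separate sentence for a participant who stops early.

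The PP definition in SAP 3 requires compliance, "defined as taking 75% or more of their study medication for the duration of the study", assessed by pill count. Protocol 6.8.2 has the same test: "taking 75% or more of their study medication for the duration of the study". Neither gives a formula or refers to SAP 6.2. Protocol 6.4.7 mentions a 75% threshold for counselling, also without a formula.

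Three other places bear on the point:

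- Protocol 6.4.3 plans that "tablets will occur daily during the 12 months of the trial".
- Protocol 6.3.7 keeps treatment stoppers in view: "Participants who prematurely discontinue study treatment will be invited to complete the planned study assessments throughout the duration of the trial".
- SAP 5.1 says that "data will be adjusted for age, gender, Skin Prick test (screening), specific IgE (screening) and compliance", and SAP 7.2.1 lists compliance among the predictors for the primary endpoint.

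**The concern.** For someone who stops at day 90, the last day of IMP taken is day 90. On the literal wording, the remaining months leave the denominator and the score describes only the first 90 days. That is not compliance over 12 months of blinded therapy, and it is not a share of study medication over the duration of the study.

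The PP set is where this could matter most. Its retention clause asks that the participant remain in the study (12 months in the Protocol, until the primary endpoint is assessed in the SAP). It does not ask that the participant remain on tablets. The 75% test is therefore the only explicit exposure requirement for a stopper who still attends the month-12 challenge. The same figure also feeds the compliance table by arm and the compliance covariate.

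**Working it through.** **Inputs.** Formula: SAP 6.2. Threshold 75%: SAP 3 and Protocol 6.8.2. Daily dosing for 12 months: Protocol 6.4.3. Arm size 22: half of the minimum of 44 to be randomised 1:1 (Protocol 6, SAP 1). Assumption: 12 months = 365 days, one tablet per day.

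**The SAP's own example.** 80 tablets taken of 100 due: 100 × 80/100 = 80%. This reproduces, but it does not test the disputed point, because it takes the 100 due tablets as given.

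**Two denominators.** Let *d* be the stop day, *a* the adherence up to that day, and *T* = 365.

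- Literal SAP 6.2 score: (*a* × *d*)/*d* = *a*
- Share of the 12-month course: (*a* × *d*)/*T*

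| Stop day | Pre-stop adherence | Tablets taken | SAP 6.2, literal | Share of 365 days |
|---|---|---|---|---|
| 90 | 100% | 90 | 100% | 90/365 = 24.7% |
| 90 | 90% | 81 | 90% | 81/365 = 22.2% |
| 180 | 100% | 180 | 100% | 180/365 = 49.3% |
| 180 | 80% | 144 | 80% | 144/365 = 39.5% |
| 270 | 100% | 270 | 100% | 270/365 = 74.0% |
| 365 (no early stop) | 80% | 292 | 80% | 292/365 = 80.0% |

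The last row shows that the rules agree for anyone who takes IMP to the planned end.

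**Where the rules disagree at 75%.** This needs *a* ≥ 0.75 and *a* × *d* < 0.75 × 365 = 273.75.

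- No missed dose: *d* < 273.75, so any stop before day 274.
- 90% pre-stop adherence: *d* < 273.75/0.90 = 304.2.
- 80% pre-stop adherence: *d* < 273.75/0.80 = 342.2.

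**Compliance table.** In an arm of 22, one day-90 stopper with no missed dose raises the arm's mean compliance by (100 − 24.7)/22 = 3.4 percentage points.

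**How many people.** Neither document predicts the number of early stoppers. Protocol 6.4.1 reports withdrawal rates of 5% (active) and 3% (placebo) in an earlier trial. Applied to 22 per arm, these give 0.05 × 22 = 1.1 and 0.03 × 22 = 0.7. The Protocol does not say whether those people attended later assessments, so this is only a rough guide.

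**The case against.** The strongest reply is that the disputed clause was meant only to keep open-label tablets out of the count. It sits below a sentence that names 12 months, it speaks of days on which the participant should have taken a tablet, and it ends at the switch to open-label Grazax. On that reading nothing conflicts. This is a fair account of what the authors may have intended, but it leaves early stoppers with no formula, so the analyst would have to choose one. The same edit is needed either way.

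A reader might infer that the plan directs early stoppers into the PP sample. The documents do not support that. SAP 3 does not cite SAP 6.2, and on its own words a day-90 stopper fails the 75% test. Misclassification requires that the 6.2 figure be used for PP. That is plausible, since both rest on a pill count and no other formula exists, but no passage says so.

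A reader might also pair the latest start with the earliest Visit 7, and the reverse, to obtain courses of 246 to 484 days. The windows are not independent in that way: the Protocol says that treatment continues for 12 months and places Visit 7 after 12 months on treatment. Such ranges should not be used.

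It also stands that numbers are small, that stoppers who decline further assessments are discharged under Protocol 6.3.7 and fail the retention clause, and that ITT membership is untouched.

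**Conclusion.** The concern holds as a defect in the compliance definition. Its effect on the trial's results is conditional. Read literally, SAP 6.2 gives 100% to a participant who took 24.7% (day 90) or 49.3% (day 180) of an assumed 365-day course. Read narrowly, it gives no value for early stoppers.

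PP membership changes only if three things occur together: the stopper attends the month-12 challenge, had at least 75% adherence before stopping, and is judged for PP by the 6.2 figure. The compliance table and the covariate take the literal value without the PP conditions, although the covariate matters only for participants with outcome data in the model.

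The withdrawal rates quoted above suggest about one person per arm at most. The effect on the PP estimate and on the covariate-adjusted estimate cannot be derived from the documents. Whether a value measured after randomisation should be adjusted for at all is a separate question, which this point does not settle.

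**What to change.** In SAP 6.2, define due days for every participant who started IMP as all days from first dose to the planned end of blinded treatment, whether or not IMP was stopped early. Set that end at 12 months after first dose, or at the actual Visit 7 date for those still on IMP at that visit. This avoids relying on a switch date, which does not exist for an early stopper. Count tablets taken over the same interval, so that numerator and denominator match. State in SAP 3 that the 75% PP criterion uses this figure.

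The cost is a short wording change and a re-derivation from the pharmacy counts that SAP 6.2 already uses, cut at the same end date. Participants who took IMP to the planned end keep the same score. The downside is that the PP sample may be slightly smaller.

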7. ENDPOINT EVALUATION

7.1 Overview of Efficacy Analysis Methods

7.1.1 Assessment Time Windows

All study visits must occur within the time limits specified below:

Atopic

Phase I (all):

Screening Visit – Visit -1, from December 2013 to April 2014

Visit – 0a, after screening and before Visit 0b

Visit - 0b, from January 2014 to April 2014

Visit – 1, after Visit – 0b

Visit – 2, from February to May 2014

Visit – 3, from March to May 2014

Visit – 4, from April to June 2014

Visit – 5, from May to August 2014

Visit – 6, from July to October, 2014

Visit – 7, from January to April 2015

Phase II (active treatment group only)

Visit – 8, 24 months after start of treatment

Visit – 9, 36 months after start of treatment

Non-Atopic

Screening Visit – September 1st to November 30th, 2014

Visit – 1 coinciding with Visit 7 at 12 months of treatment of the atopic participants

Unscheduled visits may also occur throughout the study.

The pollen season will be defined as in the protocol. Pollen counts will be quantitated retrospectively for the purposes of analysis. *Pollen season* is defined as follows:

Start of season	First 3 consecutive days at pollen count >10 grains/cm ³
End of season	First 3 consecutive days at pollen count < 10 grains/cm ³
Start of peak season	First 3 consecutive days at pollen count >30 grains/cm ³
End of peak season	First 3 consecutive days at pollen count < 30 grains/cm ³

A variable for the pollen season and peak pollen season (0 = no pollen season, 1 = pollen season, 2 = peak pollen season) will be created by the AIT team indicating when the season started and finished.

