6.4 Study medications

6.4.1 Allergen Immunotherapy Tablet (AIT)

Grazax® is a fast-dissolving tablet that is registered throughout Europe for sublingual use in patients aged 5–65 years (18–65 years in UK)^{14, 15, 16}. The tablet is administered daily for a minimum of 2 months before and during the grass pollen season. In a double-blind trial of Grazax® that included a withdrawal phase, efficacy was maintained for 2–3 years with continuous treatment^{15, 16} and at 1 year following withdrawal^{17, 18}. AIT

has been shown to be safer than the injection route. It is recommended that the first dose of Grazax® is administered in the clinic and that subsequent doses are taken independently by the patient. Local side effects of itching and swelling in the mouth are common, occurring in 50% to 60% of individuals within minutes and resolving within 1 hour with a median half-life of approximately 10 days with daily administration^{14, 15, 16}. These responses are, in general, well tolerated and require no treatment. In a recent large trial involving over 600 patients, the withdrawal rate was 5% as compared to 3% in placebo-treated patients^{14, 15}. More severe local and systemic reactions have been reported, but they are excessively rare and no fatalities have occurred¹⁹.

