6.5.14 Visits

Atopic Participants:

Scheduled Visits (screening, randomisation and blinded treatment phase):

Where possible, all study visits should occur within the time limits specified below:

Screening Visit – Visit -1, from December 2013 to April 2014.

Visit – 0a, after screening and before Visit 0b.

Visit – 0b, from January 2014 to April 2014.

Visit – 1, after Visit – 0b.

Visit – 2, from February to May 2014.

Visit – 3, from March to May 2014.

Visit – 4, from April to June 2014.

Visit – 5, from May to August 2014.

Visit – 6, from July to October, 2014

Visit – 7, from January to April 2015.

Unblinded treatment phase

Visit- 8, January-March 2016

Visit- 9, January-March 2017

Unscheduled visits:

Unscheduled visits may be performed in the event that participants experience a disease exacerbation requiring treatment or because the participant prematurely terminates from the study (see section 6.3.3).

Visit -1:**Screening visit:**

Volunteers will attend the allergy unit at the Royal Brompton Hospital for approximately 2 hours. During this visit the following will be undertaken:

- Written informed consent before any study procedures are performed.
- Demographic data (sex, date of birth, ethnic origin, medical history).
- Allergic history - record of allergic symptoms and allergic medication taken by the subject during at least the last two years.
- Physical examination and observations (weight, height, blood pressure, heart rate, peak expiratory flow rate, peak nasal inspiratory flow and spirometry).
- Participants will mark a retrospective Global evaluation (GE) visual analogue scale (VAS) (scale 0-100 mm; **Appendix 1**) and complete a retrospective GE chart (**Appendix 2**) documenting the overall severity of their hay fever symptoms during the previous pollen season.
- Participants will complete a Mini Juniper Rhinitis Quality of Life Questionnaire (mRQLQ) (**Appendix 3**) and Global evaluation scores (**Appendix 4 and 5**) corresponding to current rhinitis symptoms and medications.
- Skin prick test - standard allergen test panel as described previously.
- Blood sampling of up to 20 ml for total IgE, specific IgE to Timothy grass pollen and total blood count will be taken.
- Nasal challenge with 5,000 BU/ml Timothy grass pollen extract with TNSS recorded after 5 minutes (**Appendix 6**).
- Recording of concomitant medication.
- Evaluation of inclusion and exclusion criteria.

Visit 0a:

1st Baseline Visit:

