Around 5 months after begin of AIT/placebo and during the pollen season participants will come to the hospital for 1.5 hours. During this visit the following will be undertaken (see also **Table 4**):

- A period of 15 minutes acclimatization to hospital environment and relative inactivity.
- Participants will mark questionnaires (**Appendix 3-5**) corresponding to symptoms and rescue medication use during the current pollen season.
- Furthermore the volunteers will undergo the same procedures as in Visit 0b, plus questionnaires and with the exception of the intradermal skin test and nasal challenge.

Table 4: Time line procedures at Visit 5

Time (hr:min)		Procedure
00:00	Arrival	
00:05	Blood	Blood sample (200ml)
00:15	Pre-lavage	GE VAS; mRQLQ; SMS, secretion collection
00:20	Pre-lavage	Nasal brushing
00:25	Nasal-lavage	
00:55	Post-lavage	Secretion collection

		Nasal biopsy
--	--	--------------

GE VAS; Global Evaluation visual analogue scale

mRQLQ; mini Rhinitis Quality of Life Questionnaires

SMS; symptom medication score

Visit 6:

After 6 months of treatment and shortly after the pollen season patients will mark a retrospective GE VAS (scale 0-100 mm; **Appendix 1**), the mRQLQ (**Appendix 3**) and complete a retrospective GE chart (**Appendix 2**) documenting the overall severity of their hay fever symptoms during the previous pollen season. Also a nasal allergen challenge with 5.000 BU/ml Timothy grass pollen allergen will be undertaken. We will record the Peak Flow as well as the response to challenge for one hour at 5, 15, 30 and 60 min with TNSS + VAS and PNIF.

Time (hr:min)		Procedure
-00:15	Arrival	TNSS+VAS; GE VAS, mRQLQ, GE, PNIF; Peak Flow
00:00	Nasal Challenge	5,000 BU/ml Timothy grass pollen allergen
00:05	Early Nasal response	TNSS + VAS; PNIF
00:15	Early Nasal response	TNSS + VAS; PNIF
00:30	Early Nasal response	TNSS + VAS; PNIF
01:00	Early Nasal response	TNSS + VAS; PNIF; PeakFlow

Visit 7:

After 12 months on treatment volunteers will attend the allergy unit for a period of 2 hours in the morning and 1 hour during the evening (3 hours). During this visit the same procedures as described at Visit 0b plus a blood sample of 200 ml will be undertaken (see also **Table 2**).

Non-atopic Participants:

Scheduled Visits (screening (Visit -1), one time point assessment (Visit 1):

Screening Visit – September 1st to November 30th, 2014.

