6.6 Biomarkers

We will measure known and novel biomarkers locally in the nasal mucosa, and in peripheral blood. In atopic participants blood, nasal fluid and nasal brushings will be sampled at screening, baseline, after 4, 8 and 16 weeks and at 7 and 12 months of treatment. The same sampling will be repeated at 24 and 36 months of the open label follow-up for the treatment group. Biopsies will be performed at baseline and at 7 and 12 months of treatment, and at 24 and 36 months of open label follow-up. At screening, 20 ml of blood (10 ml blood count, and 10 ml IgE to timothy grass) will be taken. At baseline, after 4, 8 and 16 weeks, 120 ml blood will be taken (100 ml for T-, B- and dendritic cell (DC) studies and 20 ml for T- and B-cell repertoire analysis). At 7, 12 and at 24 and 36 months, 200 ml will be taken (150 ml for T-, B- and DC studies and 50 ml for T- and B-cell repertoire analysis). The healthy, non-atopic participants will present themselves after screening only once coinciding with Visit 7 at 12 months of the atopic participants. During this assessment 200 ml of blood will be taken (150 ml for T-, B- and DC-studies and 50 ml for T- and B-cell repertoire analysis). Additionally,

nasal fluid, nasal brushings and nasal biopsies will be collected. Different analyses will be performed as described below.

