7.3.2 Mechanistic Assessments

The endpoints listed below will compare the following groups using the same statistical methodology as described for the primary endpoint.

- SLIT versus SLIT Placebo
- SLIT versus SLIT Placebo versus non-atopic controls

Grass pollen specific immunological markers in serum, nasal fluid and nasal brushings will be evaluated at baseline, after 1, 2, 3 months, during the peak pollen season (at 4 months) and after 12 months of treatment. Comparisons will be made between atopic active and placebo group and at the 12 months' time point also with the non-atopic participants. Biopsies will be performed at baseline, after 12 months, 24 months of treatment and after 12 months of withdrawal.

Blood samples:

Analysis will be performed on baseline, 1, 2 and 3 months, peak pollen season and 12 months of treatment samples.

1. Immunocap (Total IgE, sIgE, sIgG4)
2. FAB-Assay
3. Basophil Activation

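### The SAP's mandatory calendar windows for Visits 3 and 4 exclude 8 and 12 weeks of treatment for most April first-dose dates, and the sampling-time labels conflict across the documents

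*SAP*

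**What the plan says.** **Windows.** SAP 7.1.1 introduces its visit list with "All study visits must occur within the time limits specified below". Protocol 6.5.14 gives the same calendar months for Visits -1 to 7 but introduces them with "Where possible, all study visits should occur within the time limits specified below". The months are: Visit 2, February to May 2014; Visit 3, March to May; Visit 4, April to June; Visit 5, May to August; Visit 6, July to October; Visit 7, January to April 2015. For Visits 2 to 7 the SAP list sets no window counted from the first tablet.

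**Starts.** Protocol section 6 has treatment beginning between January and April 2014. Protocol 6.4.3 puts the first tablet one day after Visit 0b.

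**Time labels.** Protocol 6.5.14 places Visits 2, 3 and 4 at about 4, 8 and 12 weeks, and Visit 5 at "Around 5 months after begin of AIT/placebo and during the pollen season". Protocol 6.6 gives the sampling times as "after 4, 8 and 16 weeks and at 7 and 12 months of treatment". SAP 7.3.2 has samples at 1, 2 and 3 months, then "during the peak pollen season (at 4 months) and after 12 months of treatment".

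**Biopsies.** Protocol sections 2 and 6 put the in-season biopsy at about 5 months; Protocol 6.6 and 6.8.3.3 put it at 7 months. SAP 7.3.2 says "Biopsies will be performed at baseline, after 12 months, 24 months of treatment and after 12 months of withdrawal", with no in-season biopsy.

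**Model.** SAP 7.3.2 applies the longitudinal method of SAP 7.2.1 to all markers. The predictors named there are age, gender, skin prick test, specific IgE, baseline visual analogue scale and compliance. How time is to be coded is not stated.

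**The concern.** The primary objective (Protocol 5.1) is the time course of clinical and immunological change. That requires the time attached to each sample to be known and to mean the same thing for everyone. Fixed calendar windows combined with a four-month spread of starts work against this. If the windows are obeyed literally, late starters give their 8-week and 12-week samples well before 8 and 12 weeks. If the weeks are obeyed, the SAP's rule is broken. The documents also disagree on what the nominal times are, so an analyst working by visit label cannot tell which duration a label stands for. At stake is how sharply the onset of each immunological change can be located.

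**Working it through.** **Inputs.** First doses run to 30 April 2014 (Protocol section 6). Nominal times for Visits 2 to 4 are 28, 56 and 84 days (Protocol 6.5.14). Window ends are the last day of the month named in SAP 7.1.1. Peak season is about mid-June (Protocol 6.8.3.2), taken as 15 June. The earliest first dose is 2 January, because Visit 0b starts in January and the tablet follows one day later.

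**Latest first dose that fits = window end minus nominal time.**

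| Visit | Nominal time | Window ends | Latest first dose | April dates that fit |
|---|---|---|---|---|
| 2 | 28 days | 31 May | after 30 April | 30 of 30 |
| 3 | 56 days | 31 May | 5 April | 5 of 30 |
| 4 | 84 days | 30 June | 7 April | 7 of 30 |
| 6 | 6 months | 31 October | 30 April | 30 of 30 |
| 7 | 12 months | 30 April 2015 | 30 April | 30 of 30 |

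Checks: 5 April + 56 days = 31 May; 7 April + 84 days = 30 June. Reading the SAP's 2 and 3 months as calendar months would move both limits back to 31 March, so the protocol's weeks are the more lenient reading.

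**A 30 April starter.** Visit 3 is due on 25 June and Visit 4 on 23 July. Held to the windows, treatment at Visit 3 is at most 31 days (30 April to 31 May) and at Visit 4 at most 61 days (30 April to 30 June). The 8-week sample would then come no more than 3 days after a Visit 2 held on its due date (day 28), and the 12-week sample close to 8 weeks (56 days).

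**Allowance for approximate weeks.** The documents give no tolerance. If 14 days is assumed, the latest first doses become 19 April (Visit 3) and 21 April (Visit 4). With 7 days they are 12 and 14 April.

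**Pattern of the windows.** Visits 2, 5, 6 and 7 equal January to April plus 1, 4, 6 and 12 months. Visits 3 and 4 open at plus 2 and plus 3 months but close one month earlier than that pattern implies, and Visit 3 closes in the same month as Visit 2. The closing months may be slips; the documents do not say.

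**Visit 5.** This visit is tied to the season, so exposure varies by design. At 15 June it is 164 days (164/30.44 = 5.4 months) for a 2 January start, 75 days (2.5 months) for a 1 April start and 46 days (1.5 months) for a 30 April start.

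**Labels side by side.**

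| Item | Protocol 2, 6, 6.5.14 | Protocol 6.6, 6.8.3.3 | SAP 7.3.2 |
|---|---|---|---|
| Third early sample | about 12 weeks | 16 weeks | 3 months |
| In-season sample | about 5 months | 7 months | 4 months |
| In-season biopsy | about 5 months | 7 months | not listed |

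**How many are affected.** The documents do not say. If first doses were spread evenly over the 119 days from 2 January to 30 April (my assumption), 25/119 = 21% would fall after 5 April, or about 9 of 44. The true number could be none or many more.

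**The case against.** Several stronger readings are tempting, and the case against them is good.

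- **That no April starter can comply.** Not so. First doses on 1 to 5 April fit both Visits 3 and 4, and Visits 2, 6 and 7 fit every April date. Each window can also be met by bringing the visit forward. What fails is window and nominal week together.
- **That exposure at Visits 3 and 4 must therefore differ.** It differs only if the calendar overrides the week. If the week is kept, as the protocol's softer wording allows, the result is a deviation to be listed under SAP 6.1. Part of SAP 6.2 is in the past tense, which suggests, without proving, that the SAP did not direct the 2014 visits.
- **That April starters also miss Visit 5.** This joins the SAP's mandatory wording to the protocol's 5 months. On the SAP's own 4 months every April start fits, and on 5 months a 1 April start misses by one day.
- **That the in-season biopsy has no planned use.** Protocol 6.8.3.3 plans a blinded comparison between arms at 7 months. The fault is that the SAP omits it and the protocol gives two times for it.
- **That Protocol 6.4.1 is a further conflict.** "The tablet is administered daily for a minimum of 2 months before and during the grass pollen season" reads as product description, not as a rule for visits.
- **That the season variable of SAP 7.1.1 must enter the model.** SAP 7.3.1 already uses season as an analysis period. Making it a covariate is a modelling choice.

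These points narrow the finding but do not remove it. A stated rule contradicts the stated weeks for most April dates, the labels conflict in current text, and the SAP does not say that actual time on treatment will be used.

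**Conclusion.** The point holds in limited form. Under SAP 7.1.1 as written, the windows exclude 8 weeks for first doses after 5 April and 12 weeks for those after 7 April. At the extreme, samples taken at no more than 31 and 61 days would carry those labels. The 12/16-week, 4/5/7-month and biopsy conflicts stand whatever the start date.

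A reader might infer that the primary result is at risk or that the arms are compared unfairly. The documents support neither. Twelve months falls inside the Visit 7 window for every first dose up to 30 April. Allocation is random and blinded, so start dates should balance between arms in expectation. The Visit 6 and 7 windows permit wide differences in exposure (8.1 to 15.9 months at Visit 7) but do not force them. The consequence is blurred onset timing in the mechanistic time course. It matters because the time course is the primary objective.

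This rests on reading the windows as whole calendar months, on first doses falling as late as Protocol section 6 allows, and on an unknown number of April starters. A Visit 0b on 30 April would put the first tablet on 1 May, outside that period; I have not counted that case. The SAP schedule table is too broken in extraction to settle the biopsy times, so I draw nothing from it.

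**What to change.** 1. In SAP 7.1.1, replace the mandatory calendar months for Visits 2 to 7 with windows defined from the first tablet, keeping Visit 5 tied to the season. Bring the wording into line with Protocol 6.5.14.
2. In SAP 7.3.2, analyse marker time courses by actual time since the first tablet, with arm-by-time terms. Season adjustment, if wanted, belongs at most in a sensitivity analysis: in-season status nearly coincides with Visit 5, and a three-level season variable alone takes two parameters.
3. Reconcile the 12/16-week, 4/5/7-month and biopsy passages across Protocol 6.5.14, 6.6 and 6.8.3.3 and SAP 7.1.1 and 7.3.2, and state whether the in-season biopsy is part of the SAP analysis. Which times are right is for the investigators; I take no position.

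The cost is mostly wording. The analysis needs only visit dates and the treatment start date, which SAP 6.2 already uses for compliance. The downside is a few more model parameters with about 44 randomised participants, so the form chosen for time should be simple and stated in advance.
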